10.2.3 Other Safety topics of interest

The following are AEs considered to be other safety topics of interest that require special statistical analyses. Along with the tables described, there will be a table which displays the risk difference and 95% confidence intervals for each of the topics of interest in the Initial Treatment Period. A corresponding figure (with dot plots) will be prepared.

A by-participant listing of all AEs of safety topics of interest will be presented by type of safety topics of interest.

10.2.3.1 Infections (serious, opportunistic, fungal and TB)

- **Incidence of Serious Infection TEAEs per 100 subject years by SOC, HLT and PT**

Serious infections will be identified based on MedDRA classification (SOC “Infections and infestations”) using the “Any SAE” table. A separate table does not need to be produced to summarize these events.

- **Incidence of Fungal Infection TEAEs per 100 subject years by SOC, HLT and PT**

Fungal infections will be summarized in a stand-alone table. The table will include all TEAEs (serious and non-serious) that code into the High Level Group Term (HLGT) “Fungal infectious disorders”

- **Incidence of Opportunistic Infection TEAEs per 100 subject years by SOC, HLT and PT**

Opportunistic infections (including tuberculosis) will be summarized in a stand-alone table.
The table will include all TEAEs identified using UCB-defined search criteria .

The following steps will be followed for identifying and reviewing opportunistic infections:

Identification Process

The steps below outline 2 ways in which opportunistic infections (or potential opportunistic infections) can be identified:

Step 1: Refer to column B of the spreadsheet, which identifies the PTs to be classified as opportunistic infections using either a single 'x' or a double 'xx'.

- All TEAEs that code to a PT flagged with a single 'x' need to also be serious to be considered an opportunistic infection.
- All TEAEs that code to a PT flagged with a double 'xx' are considered to be an opportunistic infection, regardless of seriousness.

Step 2: Refer to column C of the spreadsheet, which identifies the PTs that need to be evaluated on a case-by-case basis by the study physician to determine whether or not it is an opportunistic infection. If column C has a single 'x', then the corresponding preferred term will be flagged for case-by-case review by the study physician.

Review Process

Opportunistic infections for a given study will be reviewed on the following occasions:

- At quarterly Infectious Disease Committee (IDC) Meetings, listings will be produced for each study (see details below) and reviewed by the corresponding study physician ahead of the IDC Meeting. These listings will be posted as part of the broader Safety Signal Detection (SSD) deliverable to a folder named for the given quarter (eg, 2018Q4) on the SharePoint. They will be based on the same data cut as the one used for SSD and will be delivered at the same time as the SSD outputs. The IDC will then agree on the final adjudication for each potential opportunistic infection.
- For each study, a final listing for opportunistic infections (in the format described below) will be produced and agreed upon between the study physician and the IDC prior to finalizing the database.

In each of the circumstances described above, the study programming team will produce an Excel listing that will be provided to the project lead statistician, project lead programmer, and to the study physician (who will subsequently provide it to the IDC). The Excel listing will contain the following columns (using the descriptions below as the column headings in the Excel listing):

- Study ID
- Unique Participant ID
- AE Term (Verbatim)
- AE Preferred Term
- AE System Organ Class
- AE High Level Term

- AE Low Level Term
- Date of Onset
- Outcome of Adverse Event
- Date of Outcome
- TEAE Flag
- Serious Adverse Event?
- Relationship to Study Medication
- Intensity
- Action Taken with IMP
- Opportunistic Infection – Automatic
- Opportunistic Infection – Manual Review
- Flag
- Data Cut Date
- Opportunistic Infection – Final Adjudication

Note the following about the final 5 variables in this listing:

- *Opportunistic Infection – Automatic*: This is flagged as “Y” if the criteria for automatic selection as described in “Step 1” of the identification process are met.
- *Opportunistic Infection – Manual Review*: This is flagged as “Y” if the criteria for case-by-case selection as described in “Step 2” of the identification process are met.
- *Flag* – This has a value of either “NEW” or “OLD”. It is marked as “NEW” if the event is appearing for the first time in that run of the listing. Otherwise, if it has appeared previously, it is marked as “OLD”. Unique records are determined by USUBJID AESPID for purposes of identifying whether an event has been modified from a previous run.
- *Date* – Only for cases where Flag is “NEW”, this field will be populated with the data cut date for that particular run of the listing.
- *Opportunistic Infection – Final Adjudication* – For new events, this is always left blank by the programmers. It will be completed by the study physician/IDC for every event that appears in the listing. For events adjudicated as opportunistic, the field will be populated with a “Y”.

Following each review by the study physician and IDC, the Opportunistic Infection – Final Adjudication column will be completed (as described above), and the spreadsheets for each study will be returned to the study programming team via e-mail (coordinated by the IDC secretary). Then, for subsequent runs of the listing, the study programming teams will incorporate adjudications from previous runs.

10.2.3.2 Malignancies

- **Incidence of Malignant or Unspecified Tumours TEAEs per 100 subject years by SOC, HLT and PT**

These events will be presented in the following tables:

- One table will be based on the criteria Standardized MedDRA Query (SMQ) = “Malignant or unspecified tumours (SMQ)”
- One table will be based on the criteria SMQ = “Malignant tumours (SMQ)”.

SMQ search will include all TEAEs which code to a PT included in the Scope=Narrow group within each SMQ.

Note that the events included in the “Malignancies” table will be a subset of the events included in the “Malignancies (including unspecified)” table. While the “Malignant tumours (SMQ)” is most relevant, “Malignant or unspecified tumours (SMQ)” must be reviewed for potential malignancies.

The output tables will include 2 different overall incidence rows:

- The first overall incidence row will summarize “Any Malignancy” and this row will summarize the incidence of all AEs flagged for inclusion in the table (using the appropriate SMQ depending on the table), regardless of the HLT it codes to.
- The second overall incidence row will summarize “Any Malignancy excluding non melanotic skin cancers HLT” and this row will summarize the incidence of AEs flagged for inclusion in the table (using the appropriate SMQ depending on the table), excluding those which code to an HLT of “skin neoplasms malignant and unspecified (excl melanoma)”.

10.2.3.3 Major adverse cardiac event

- **Incidence of Adjudicated Major Cardiac Event (MACE) TEAEs per 100 subject years by SOC, HLT and PT**

Potential cardiovascular events are adjudicated by the independent Cardiovascular Event Adjudication Committee (CV-CAC) according to the CV-CAC Charter (version 6.0).

Adjudicated events are classified by the CV-CAC to one of the event types as defined in [Table 10-1](#). The classification of an event as a Major Adverse Cardiac Event (MACE) is also determined by the CV-CAC. Events which are classified by the CV-CAC as any of the event types identified in the third column of [Table 10-1](#) will be considered an extended MACE. Note that extended MACE is determined programmatically and includes a broader scope definition of MACE.

MACE as determined by the CV-CAC will be presented in a table and listing. Extended MACE will be presented separately in a table and listing.

Another table and listing will present the adjudicated cardiovascular events by type. For each cardiovascular event type, the individual PTs which fall within each event type will be summarized. This listing will indicate whether each event was determined to be a MACE and/or an extended MACE.

Additionally, a listing of all events identified for potential review by the CV-CAC will be produced. This listing will indicate whether each event was identified by the CV-CAC Chair for full committee review.

Table 10-1: Cardiovascular event classifications

Event Type Code	Event Type	Extended MACE
1	Non-Fatal Myocardial Infarction (MI)	Yes
2	Non-Fatal Stroke: hemorrhagic	Yes
3	Non-Fatal Stroke: ischemic	Yes
4	Non-Fatal Stroke: embolic	Yes
5	Non-Fatal Stroke: undeterminable	Yes
6	Hospitalization or ER for Unstable Angina with urgent revascularization	Yes
7	Hospitalization or ER for Unstable Angina without urgent revascularization	No
8	Hospitalization for Heart Failure	Yes
9	Transient Ischemic Attack (TIA)	No
10	Coronary Revascularization Procedures (e.g. percutaneous coronary intervention, coronary artery bypass grafting)	Yes
11	Urgent Revascularization Procedures (i.e. due to symptoms of brain ischemia or pending infarction)	Yes
12	Arrhythmia (not associated with ischemia)	No
13	Peripheral Arterial Event	No
14	Venous Thromboembolic Event: pulmonary embolism (PE)	No
15	Venous Thromboembolic Event: deep vein thrombosis (DVT)	No
16	Venous Thromboembolic Event: PE and DVT	No
17	Other CV Event	No
18	Death due to Myocardial Infarction (MI)	Yes
19	Death due to Stroke	Yes
20	Sudden Cardiac Death	Yes

Table 10–1: Cardiovascular event classifications

Event Type Code	Event Type	Extended MACE
21	Other CV Death (e.g. heart failure, pulmonary embolism, cardiovascular procedure-related)	Yes
22	Cardiovascular: Undetermined Cause of Death (i.e. cause of death unknown)	Yes
23	Non-Cardiovascular Death	No
24	Non-Cardiovascular Event	No
99	Inadequate information to adjudicate	No

CV=Cardiovascular; DVT=Deep Vein Thrombosis; ER=Emergency Room; MACE= Major Adverse Cardiac Event; MI=Myocardial Infarction; PE=Pulmonary Embolism; TIA=Transient Ischemic Attack.

MACE is determined by the adjudication committee and is not identified programmatically based on event type.

10.2.3.4 Neutropenia

- Incidence of Neutropenia TEAEs per 100 subject years by SOC, HLT and PT**

This table will be based on the following PTs (regardless of seriousness):

- Autoimmune neutropenia
- Band neutrophil count decreased
- Cyclic neutropenia
- Febrile neutropenia
- Idiopathic neutropenia
- Neutropenia
- Neutropenic infection
- Neutropenic sepsis
- Neutrophil count decreased

10.2.3.5 Suicidal Ideation and Behavior

- Incidence of Suicidal Ideation or Behavior TEAEs per 100 subject years by SOC, HLT and PT**

Potential neuropsychiatric events are adjudicated by the independent Neuropsychiatric Adjudication Committee according to the Neuropsychiatric Adjudication Committee (version 8.0). Adjudicated events are classified by the Committee as Suicidal or Non-suicidal.

Adjudicated events are also further classified by the Committee to one of the event types as defined in [Table 10–2](#). Suicidal Ideation and Behavior (SIB) is defined as events classified by the Committee as Suicidal.

A table and listing will present SIB events.

Another table and listing will present the adjudicated neuropsychiatric events by type. For each neuropsychiatric event type, the individual PTs which fall within each event type will be summarized. This listing will indicate whether each event was determined to be Suicidal or Non-Suicidal. For event type suicidal ideation, the listing will also indicate if intent was present and if the suicidal ideation was clinically significant.

Additionally, a listing of all events identified for potential review by the Committee will be produced. This listing will indicate whether each event was identified by the Neuropsychiatric Event Adjudication Committee Chair for full committee review.

Table 10–2: Neuropsychiatric event classifications

Event Type Code	Event Classification	Event Type
1	Suicidal	Suicidal events/completed suicide
2	Suicidal	Suicide attempt
3	Suicidal	Preparatory acts toward imminent suicidal behavior
4	Suicidal/Non-suicidal ^a	Suicidal ideation
7	Non-suicidal	Nonsuicidal Self-injurious behavior
8	Non-suicidal	Nonsuicidal Other
99	Not applicable	Inadequate information to adjudicate

^a Suicidal ideation event types can be classified by the Neuropsychiatric Adjudication Committee as Suicidal or Non-suicidal depending on whether intent to die was present.

10.2.3.6 Inflammatory bowel disease

- Incidence of Inflammatory Bowel Disease TEAEs per 100 subject years by SOC, HLT and PT**

Selected gastrointestinal events are adjudicated by the independent Inflammatory Bowel Disease (IBD) Adjudication Committee (IBD-CAC) according to the IBD-CAC Charter (version 3.0). Adjudicated events are classified by the IBD-CAC into one of the diagnostic types as defined in [Table 10–3](#). The events will further be classified as definite, probable or possible IBD.

An overview of adjudicated IBD events will be stratified by subjects with or without a previous medical history of IBD. Previous medical history of IBD will be determined using the information recorded on the History of IBD CRF page ("Does subject have a history of IBD?"). This overview table will present events adjudicated by the IBD-CAC as either possible, probable or definite IBD. Definite and probable IBD will also be aggregated and summarized in this table. In addition, this table will summarize each IBD event classification (possible, probable or definite) separately.

Another table and listing will present the adjudicated IBD events by type. For each IBD event type, the individual PTs which fall within each event type will be summarized.

Additionally, a listing of all events identified for potential review by the IBD-CAC will be produced. This listing will indicate whether each event was identified by the IBD-CAC Chair for full committee review.

A further supportive listing will present the individual diagnostic criteria met for each adjudicated IBD event.

Table 10–3: IBD event classifications

Event Type Code	Event Type (Classification and diagnosis)	Classification
1	Possible Inflammatory Bowel Disease – Crohn's Disease	Possible
2	Probable Inflammatory Bowel Disease – Crohn's Disease	Probable
3	Definite Inflammatory Bowel Disease – Crohn's Disease	Definite
4	Possible Inflammatory Bowel Disease – Ulcerative Colitis	Possible
5	Probable Inflammatory Bowel Disease – Ulcerative Colitis	Probable
6	Definite Inflammatory Bowel Disease – Ulcerative Colitis	Definite
7	Possible Inflammatory Bowel Disease – type unclassified	Possible
8	Probable Inflammatory Bowel Disease – type unclassified	Probable
9	Definite Inflammatory Bowel Disease – type unclassified	Definite
10	Symptoms not consistent with Inflammatory Bowel Disease	Not applicable
11	Possible Inflammatory Bowel Disease – Microscopic Colitis	Possible
12	Probable Inflammatory Bowel Disease – Microscopic Colitis	Probable
13	Definite Inflammatory Bowel Disease – Microscopic Colitis	Definite
14	Possible Inflammatory Bowel Disease – no further differentiation possible	Possible
15	Probable Inflammatory Bowel Disease – no further differentiation possible	Probable
16	Definite Inflammatory Bowel Disease – no further differentiation possible	Definite
99	Not enough information to adjudicate	Not applicable

IBD=inflammatory bowel disease.

Note: IBD diagnoses of “microscopic colitis” and “no further differentiation possible” were added in an adjudication charter amendment, accounting for the event type numbering.

10.2.3.7 Hypersensitivity (including anaphylaxis)

- Incidence of Anaphylactic Reaction TEAEs per 100 subject years by SOC, HLT and PT**

A separate table will be prepared based on the MedDRA anaphylaxis Algorithm (see Appendix 1) for acute anaphylactic events (reported on the same day as when an injection was administered or 1 day after). An AE glossary table will also be produced to summarize the MedDRA coding for these events. The glossary table will include the following fields: reported term, PT, LLT, HLT, and SOC.

A separate table will be prepared to summarize hypersensitivity events, identified using the SMQ “Hypersensitivity (SMQ)”. All TEAEs which code to a PT included in the Scope=Narrow search will be included in this table. In addition, a separate table will be prepared to summarize serious hypersensitivity events, identified using the SMQ “Hypersensitivity (SMQ)”. All serious TEAEs which code to a PT included in the Scope=Narrow search will be included in this table. An AE glossary table will also be produced to summarize the MedDRA coding for these events. The glossary table will include the following fields: reported term, PT, LLT, HLT, and SOC.

Furthermore, a separate table will be prepared to summarized injection site reactions, identified using the HLTs: “Administration site reactions NEC” and “Injection site reactions”.

10.2.3.8 Hepatic events and PDILI

- Incidence of hepatic events TEAEs per 100 subject years by SOC, HLT and PT**

A table for hepatic events will be created based on the SMQ of “Drug related hepatic disorders - comprehensive search (SMQ)”. However, these 2 sub-SMQs are to be excluded: “Liver neoplasms, benign (incl cysts and polyps) (SMQ)” and “Liver neoplasms, malignant and unspecified (SMQ)”. For each of the above SMQs, include all TEAEs which code to a PT included in the Scope=Broad and/or Scope=Narrow.

Note that all AEs meeting the above criteria are to be included. It will not be limited to events that the investigator determined to be related to study drug.

Cases of potential Hy’s Law will be reported separately in a liver function test table.

10.3 Clinical laboratory evaluations

Laboratory values, including markedly abnormal laboratory values will be presented descriptively by treatment group for the SS, MS, and AMS.

The markedly abnormal tables and those based on common terminology criteria for AEs (CTCAE) grade will be produced only for selected laboratory variables.

For tables where data are summarized by visit, unscheduled and repeat visits will not be summarized, but these data will be included in listings. For tables where multiple measurements over a period of time are considered (as in shift tables), unscheduled and repeat visits will be considered as long as they were collected in the period being summarized (values observed more than 140 days after the last administration of study medication are not considered). All summaries will be presented in SI units and will be based on observed case values. In the case where laboratory values are below the LLQ, then these will be set to the midpoint between 0 and the lower limit of quantification for the purpose of summarizing the data. The following summaries are required:

- A summary of the absolute and change from Baseline values in each laboratory variable by treatment group and visit**

- A summary of the number and percentage of participants experiencing markedly abnormal values at any time while on treatment (assessment on or following the first dose of study treatment through the minimum of period of interest (Week 16) or date of last dose + 140 days) by laboratory variable and treatment group. Two separate tables will show results for the Initial Treatment Period (for the SS) and the Initial and Maintenance Treatment Period (for the AMS).
- A summary of the number and percentage of participants with a given CTCAE grade (0,1,2,3, or 4) based on minimum/maximum post-baseline value by laboratory variable and treatment group. Two separate tables will show results for the Initial Treatment Period (for the SS) and the Initial and Maintenance Treatment Period (for the AMS).
- A shift table of the number and percentage of participants experiencing CTCAE grade 0,1,2,3, or 4 values (as applicable) at Baseline to maximum post-Baseline CTCAE grade, by laboratory variable and treatment group. Two separate tables will show results for the Initial Treatment Period (for the SS) and the Initial and Maintenance Treatment Period (for the AMS).
- A by-participant listing of all laboratory data (including urinalysis) will be provided. This listing will be presented by treatment group and will include: center, participant identifier, age, sex, race, weight, visit, laboratory variable, result (with abnormal values flagged as “L” or “H” accordingly) and unit.

Markedly abnormal values are defined as those with a severity of Grade 3 and above based on the CTCAE criteria Version 4.03. Definitions of markedly abnormal values using the Grade 3 cut points are given in the tables below for age ranges of ≥ 17 years [Table 10-4](#) for markedly abnormal liver function test values, [Table 10-5](#) for markedly abnormal biochemistry values and [Table 10-6](#) for markedly abnormal hematology values). Tables summarizing markedly abnormal values will include a summary (counts and percentages) of markedly abnormal labs observed at any time while on treatment (ie, treatment-emergent markedly abnormal [TEMA]). For this summary, Baseline values and values observed more than 140 days after the last administration of study medication are not considered. The laboratory results classified as Grade 3 or Grade 4 will be summarized and listed separately.

Table 10-4: Definitions of Markedly Abnormal Liver Function Values

Parameter name	Conventional		Standard		Abnormal Designation
	Unit	Criteria	Unit	Criteria	
ALP	U/L	$>5.0 \times \text{ULN}$	U/L	$>5.0 \times \text{ULN}$	AH
ALT	U/L	$>5.0 \times \text{ULN}$	U/L	$>5.0 \times \text{ULN}$	AH
AST	U/L	$>5.0 \times \text{ULN}$	U/L	$>5.0 \times \text{ULN}$	AH
Total Bilirubin	mg/dL	$>3.0 \times \text{ULN}$	umol/L	$>3.0 \times \text{ULN}$	AH
GGT	U/L	$>5.0 \times \text{ULN}$	U/L	$>5.0 \times \text{ULN}$	AH

Table 10–5: Definitions of Markedly Abnormal Biochemistry Values

Parameter name	Conventional		Standard		Abnormal Designation
	Unit	Criteria	Unit	Criteria	
Creatinine ¹	mg/dL	> 3.0 x Baseline or >3.0 x ULN	umol/L	> 3.0 x Baseline or >3.0 x ULN	AH
Glucose	mg/dL	<40 >250	mmol/L	<1.7 >13.9	AL AH
Calcium	mg/dL	>12.5 <7.0	mmol/L	>3.1 <1.75	AH AL
Magnesium	mg/dL	>3.0 <0.9	mmol/L	>1.23 <0.4	AH AL
Potassium	mmol/L	>6.0 <3.0	mmol/L	>6.0 <3.0	AH AL
Sodium	mmol/L	>155 <130	mmol/L	>155 <130	AH AL
Cholesterol	mg/dL	>400	mmol/L	>10.34	AH

1 The markedly abnormal definitions for creatinine are based on the logical or, if either criterion is met the creatinine value will be designated as abnormal high.

Table 10–6: Definitions of Markedly Abnormal Hematology Values

Parameter name	Conventional		Standard		Abnormal Designation
	Unit	Criteria	Unit	Criteria	
Hemoglobin	g/dL	<8.0 >4.0 above ULN	g/L	<80 >40 above ULN	AL AH
Lymphocytes Absolute	10 ⁹ /L	<0.5 >20.0	10 ⁹ /L	<0.5 >20.0	AL AH
Neutrophils Absolute	10 ⁹ /L	<1.0	10 ⁹ /L	<1.0	AL
Platelets	10 ⁹ /L	<50	10 ⁹ /L	<50	AL
WBC/Leukocytes	10 ⁹ /L	<2.0 >100	10 ⁹ /L	<2.0 >100	AL AH

Abbreviations: AH=abnormal high; AL=abnormal low; ALP = alkaline phosphatase; ALT= alanine aminotransferase; AST = aspartate aminotransferase; dL = deciliter; GGT: gamma-glutamyltransferase; L = liter; mg = milligram; mmol = millimoles; µg = microgram; ULN = upper limit of normal, WBC=white blood cells.

The table for markedly abnormal liver function tests (LFTs) will contain data beyond the CTCAE Grade 3 thresholds outlined in [Table 10–4](#) above in order to allow for a more thorough review of elevated LFTs. There will be 1 table, which will list the count and percentage of participants meeting the below criteria at any time during the study:

- AST: >3xULN, >5xULN, >8xULN, >10xULN, >20xULN
- ALT: >3xULN, >5xULN, >8xULN, >10xULN, >20xULN
- AST or ALT: >3xULN, >5xULN, >8xULN, >10xULN, >20xULN
- Total Bilirubin: >1.5xULN, >2xULN
- ALP: >1.5xULN

For any participant with at least one markedly abnormal LFT (AST >3xULN, ALT >3xULN, bilirubin >3xULN, or ALP >1.5xULN) the New Ratio (nR) will be calculated as the ratio of either ALT or AST (whichever is higher) to ALP, all expressed as multiples of their ULN as follows:

- $nR = [\text{maximum}(\text{AST}/\text{ULN} \text{ or } \text{ALT}/\text{ULN})]/(\text{ALP}/\text{ULN})$

Any pDILI will be summarized (all criteria must be met at the same assessment):

- (AST or ALT > 3xULN) and Total Bilirubin > 1.5xULN
- (AST or ALT > 3xULN) and Total Bilirubin > 2xULN

In addition, a table will be produced to summarize potential Hy's Law cases. The following definition will be used in that table:

- [AST \geq 3xULN or ALT \geq 3xULN] and Total Bilirubin \geq 2xULN in the absence of ALP \geq 2xULN

In order to meet the above potential Hy's Law criteria, a participant must experience the elevation in bilirubin and ALT or AST (and the absence of ALP elevation, if applicable) at the same assessment. For example, a participant who experiences a \geq 2 x ULN elevation of bilirubin at one visit and a \geq 3xULN elevation in ALT (or AST) at a subsequent visit has not fulfilled the Hy's Law criteria.

Potential hepatotoxicity (meeting one of the PDILI or Hy's Law laboratory criteria at least once) will be considered with and without symptoms potentially associated with hepatitis or hypersensitivity according to the investigator (reported on the Symptoms of Hepatitis and Hypersensitivity CRF page).

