10.4 Vital signs, physical findings, and other observations related to safety

10.4.1 Vital signs

The following vital signs variables will be summarized: systolic blood pressure (mmHg), diastolic blood pressure (mmHg), body temperature (°C) and heart rate (beats/min). The following summaries will be provided for the SS:

- A summary of the absolute and change from Baseline value for each vital sign variable by treatment group and visit.
- A summary of the number and percentage of participants experiencing at least 1 markedly abnormal value for a vital sign variable as defined in [Table 10-7](#), by treatment group and period (Initial Treatment Period [SS], and Initial and Maintenance Treatment Period [AMS]).

Unscheduled and repeat visits will be considered as long as they were collected in the period being summarized (values observed more than 140 days after the last administration of study medication are not considered).

Table 10–7: Definitions of Markedly Abnormal Blood Pressure Values

Parameter (unit)	Markedly Abnormal Low	Markedly Abnormal High
Systolic blood pressure (mmHg)	<90 and a decrease from Baseline of ≥ 20	>180 and an increase from Baseline of ≥ 20
Diastolic blood pressure (mmHg)	<50 and a decrease from Baseline of ≥ 15	>105 and an increase from Baseline of ≥ 15

A by-participant listing of all vital signs data will be provided. This listing will be presented by treatment group and will include: center, participant identifier, age, sex, race, weight, visit, vital sign variable and result (with abnormal values flagged as “L” or “H” accordingly).

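### The treatment-emergent markedly abnormal laboratory count sets no condition on Baseline grade, so a Grade 3 or 4 abnormality that predates dosing and persists is counted as emergent

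*SAP*

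**What the plan says.** All of the following is in SAP Section 10.3 unless stated otherwise.

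- Threshold: "Markedly abnormal values are defined as those with a severity of Grade 3 and above based on the CTCAE criteria Version 4.03". Tables 10-4 to 10-6 list the cut points.
- Summary: counts and percentages of "markedly abnormal labs observed at any time while on treatment (ie, treatment-emergent markedly abnormal [TEMA"]).
- Role of Baseline: "For this summary, Baseline values and values observed more than 140 days after the last administration of study medication are not considered".
- Table specification: participants "experiencing markedly abnormal values at any time while on treatment (assessment on or following the first dose of study treatment", up to the end of the period or last dose plus 140 days. One table covers the Initial Treatment Period on the Safety Set. The other covers the Initial and Maintenance Treatment Period on the Active Medication Set (AMS).
- The only laboratory criterion in Tables 10-4 to 10-6 that refers to Baseline is creatinine: "> 3.0 x Baseline or >3.0 x ULN".
- A separate shift table shows CTCAE grade "at Baseline to maximum post-Baseline CTCAE grade, by laboratory variable and treatment group", for the same two periods and analysis sets.

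Elsewhere, Table 10-7 (Section 10.4.1) defines markedly abnormal blood pressure by a cut point plus a change, for example "and a decrease from Baseline of" a stated amount. Section 10.2.1 makes an adverse event treatment-emergent only if it starts on or after the first dose.

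**The concern.** The term treatment-emergent says that something appeared or got worse after dosing. The rule in Section 10.3 tests only whether a Grade 3 or higher value exists after dosing. Someone with, say, glucose above 13.9 mmol/L or hemoglobin below 80 g/L both before the first dose and at a later visit has no new abnormality, yet enters the TEMA count.

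At stake is the meaning of a reported safety percentage: it mixes pre-existing disease with on-treatment change. In the Initial Treatment Period the placebo column gives a yardstick for the pre-existing part. In the combined-period AMS table it does not. The AMS is limited to participants who received bimekizumab, and the placebo arm switches to bimekizumab at Week 16.

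**Working it through.** The SAP states no figure on this point, so there is none to reproduce. The check is a reading of the rule, followed by a sizing under stated assumptions.

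**Trace of the rule.** A participant counts if any value dated from first dose to the end of the window is Grade 3 or above. The outcomes for one parameter and direction are:

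| Baseline grade | Worst on-treatment grade | Counted as TEMA? | New or worse? |
|---|---|---|---|
| Below 3 | 3 or 4 | Yes | Yes |
| 3 | 4 | Yes | Yes |
| 3 | 3 | Yes | No |
| 4 | 3 or 4 | Yes | No |
| 3 or 4 | Below 3 | No | No |

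The third and fourth rows are the fault.

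**Does any other text prevent it?**

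1. The sentence that leaves out Baseline values removes the Baseline measurement from the count. It does not remove a participant who was abnormal at Baseline and is abnormal again later.
2. Apart from creatinine, the cut points in Tables 10-4 to 10-6 make no reference to Baseline. For creatinine the Baseline criterion is joined by a logical *or* (Table 10-5, footnote 1). A value above 3 times ULN qualifies alone, so nobody is excluded.
3. The shift table displays Baseline grade but does not change the TEMA count. Tables 12-1 and 12-2 contain no grades for ALT, AST, ALP, GGT, bilirubin or glucose. For these the SAP prints the Grade 3 cut point (Tables 10-4 and 10-5) but not the full grading that a shift table needs.

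**Size, under assumption.** Let *p* be the proportion at Grade 3 or above at Baseline for a parameter, and *s* the share of those with at least one such value again on treatment. The SAP gives neither, so *p* = 0.5% to 2% and *s* = 50% to 100% are assumed. The excess count in an arm of size *n* is *n* × *p* × *s*, and the excess percentage is *p* × *s*:

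- low: 0.005 × 0.5 = 0.25%
- high: 0.02 × 1 = 2%

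Planned sizes are from Section 2.4, with the two Q2W arms pooled for the Initial Treatment Period as in Section 3.6:

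| Group | *n* | Low | High |
|---|---|---|---|
| Bimekizumab Q2W (pooled) | 280 | 0.7 | 5.6 |
| Bimekizumab Q4W | 140 | 0.35 | 2.8 |
| Placebo | 70 | 0.175 | 1.4 |

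The bimekizumab total is 1.05 to 8.4 of 420. The percentage is the same in every row.

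**Related inconsistency: high hemoglobin.** Table 10-6 flags a value more than 40 g/L above ULN. Table 12-2 applies that limit only when Baseline is not above ULN; otherwise Grade 3 needs a rise of more than 40 g/L from Baseline. Take a Baseline 5 g/L above ULN and a later value 42 g/L above ULN. The rise is 42 − 5 = 37 g/L, which is Grade 2 in Table 12-2, yet Table 10-6 calls the value markedly abnormal. Section 10.3 says markedly abnormal means Grade 3 or above, so the two tables disagree.

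**The case against.** The strongest reply is that little is lost. The shift table covers the same periods and sets, so an unchanged Grade 3 participant sits in a visible cell. Change from Baseline by visit and a full laboratory listing are also planned. Section 10.3 names CTCAE 4.03, so the grades missing from Appendix B have a stated source. The summary is descriptive and no test depends on it. Most of this stands, and it keeps the point modest. It does not correct the count itself, which still carries a label that it does not meet.

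A reader might draw four stronger conclusions that the SAP does not support:

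- *Everyone abnormal at Baseline is reported as emergent.* No: a participant whose on-treatment values all fall below Grade 3 is not counted.
- *With six bimekizumab participants for each placebo participant, pre-existing abnormalities will appear only under bimekizumab and create a false signal.* That pattern comes from the allocation ratio and the rarity of the event, and genuinely new background events at the same rate would show it equally often. The table reports percentages by arm, and randomization balances Baseline abnormality in expectation.
- *The blood pressure rule contradicts the laboratory rule.* Table 10-7 uses its own cut points and is not labelled treatment-emergent. It shows that the SAP uses change from Baseline elsewhere, not that the two rules must match.
- *This is the principal laboratory result.* It is one of several required summaries. The laboratory endpoint in Section 2.2.3.2 is absolute change from Baseline.

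A simple fix that admits only participants below Grade 3 at Baseline would also drop those who worsen from Grade 3 to Grade 4. The present rule does capture them. That objection is right and shapes the fix below.

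**Conclusion.** The concern holds as a fault in how one reported count is defined and labelled. Section 10.3 counts a persisting Grade 3 or 4 abnormality as treatment-emergent, and nothing else in the SAP prevents it. TEMA percentages are overstated in every arm, by 0.25 to 2 percentage points per parameter if 0.5% to 2% of participants are Grade 3 or above at Baseline and half to all remain so. Those inputs are assumptions, and the true size depends on who was enrolled.

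No bias between arms is expected in the Initial Treatment Period. The consequence is greater in the combined-period AMS table, which has no placebo control for the full period, and for liver tests and glucose, where Appendix B gives no grades to support the shift table. The hemoglobin disagreement between Tables 10-6 and 12-2 is a separate, small inconsistency.

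**What to change.** In Section 10.3:

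1. Define TEMA as a post-Baseline value of Grade 3 or higher that is a higher grade than at Baseline for the same parameter and direction. That means Baseline below Grade 3, or Grade 3 worsening to Grade 4.
2. Keep a separate row for any post-Baseline value of Grade 3 or higher, regardless of Baseline, so that no case disappears from the table.
3. Add to Appendix B the CTCAE 4.03 grades for the liver tests and glucose. Both the Grade 3 to Grade 4 comparison and the shift table need them.
4. Align the high-hemoglobin criterion in Table 10-6 with Table 12-2, or state why they differ.

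The cost is a short definition, a filter in the program, some added rows in Appendix B and one more row per parameter in the output. No new data are needed.
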